**Emory University Investigator**

[name], Assistant Professor of Medicine, Department of Cardiology

**Introduction/Background:** Catheter ablation of cardiac arrhythmia is performed to offer symptomatic relief from a variety of atrial, ventricular and atrio-ventricular rhythms. Irrigated ablation catheters are commonly used for ablation of arrhythmias arising from the left heart and coronary sinus, to mitigate potentials risks of catheter ablation, including char formation on the catheter tip. These catheters contain internal channels allowing for infusion of an external fluid directly to the tip of the catheter, where the fluid is sprayed through numerous end holes allowing for cooling of the catheter ablation tip. Normal and half normal saline are the most commonly used irrigant fluids.

Fluid filled catheters are also the primary tool utilized to assess intravascular and intracardiac pressures and hemodynamics in the cardiac catheterization suite and intensive care unit. Intravascular hemodynamics allow assessment and diagnosis of a variety of cardiac conditions which are commonly found in patient undergoing catheter ablation, including congestive heart failure, diastolic dysfunction, and valvular heart disease. However, the fluid filled catheters commonly used for these assessments are single lumen and generally have a minimal diameter of 5 French for intracardiac catheters. Principles of fluid mechanics are characterized by Poiseuille's law and Bernoulli's law, which suggest that the radius of the fluid filled catheter will impact the reliability of the reading. "Dampening" of pressure waveforms are observed in smaller diameter catheters and may lead to underestimation of peak pressure and overestimation of the nadir pressure gradient.

It is unknown if transduction of pressures from the tip of an irrigated ablation catheter will yield equivalent results compared to use of a single 5F lumen catheter.

The purpose of this study is to test the hypothesis that transduction of intracardiac pressures using an irrigated ablation catheter placed as standard of care for the ablation procedure is equivalent to transduction of pressures using a standard 5F balloon tipped PA catheter placed only for this research study.

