### **Objectives:**

The main objective of this study is to take intracardiac pressure measurements and pressure waveforms with both a "gold standard" balloon tipped pulmonary artery catheter placed for this study and an irrigated ablation catheter placed as standard of care for the procedure in order to evaluate the following 2 questions:

1. Determine accuracy of intracardiac pressure measurements as assessed by the balloon tipped pulmonary artery catheter and by an irrigated ablation catheter.
2. Determine accuracy of intracardiac pressure waveforms measured by the balloon tipped pulmonary artery catheter and by an irrigated ablation catheter.

**Research Design:** The study will occur in patients undergoing routine cardiac ablation of his/her arrhythmia with planned use of an irrigated ablation catheter. The irrigation port of the irrigated ablation catheter will be connected via a three way stop cock to the irrigation tubing via 1 port and to a pressure transducer via the second port (see figure 1). All ports will be flushed through to the tip of the catheter to ensure no air in the line, per standard protocol. The pressure transducer will be leveled and “zeroed” per routine using CARDIOLAB software. A 5F MPA catheter will be prepared in similar fashion to the ablation, without an irrigant line running. “Zero” will be confirmed by positioning each catheter next to each other and assessing for equal waveform values.

Ablation and catheter manipulation will be done per routine under the supervision of a qualified electrophysiologist. The pressure line will be left “off” with the stopcock during the EP study and ablation, and whenever pressure assessment is not being performed.

After completion of ablation/study, the ablation catheter will be serially positioned in the cardiac chambers (left OR right atrium, left OR right ventricle). Because pressure values, slopes and characteristics are similar between the atria and ventricles, all 4 chambers will not be sampled. The stop cock will be turned to the pressure transducer and waveforms will be stored corresponding to each chamber. Next, the catheter will be removed and replaced with a 5F balloon tipped PA catheter which will be positioned under fluoroscopic guidance in each previously evaluated chamber. The placement of the balloon tipped PA catheter and measurements for this study will take about 10 additional minutes.

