Figure 1: Stop cock connected to irrigant port of ablation catheter. In current position, standard irrigant is flowing through catheter via manufacturer pump.

[figure not shown]

Figure 2: Stop cock is now turned to open the irrigant port to the pressure sensing line. In this configuration, pressure is transduced from the tip of the catheter.

**Risks/benefits:** Risks of this procedure are related to insertion of the balloon tipped pulmonary catheter into the heart. The catheter will be placed through access sites in the right and left femoral vein which are used for the ablation (no new vein access is required for this study)

Insertion risks include <1% risk of stroke, infection, damage to heart or valves or damage to conduction centers of heart.

Potential benefits to the subject include assessment and analysis of intracardiac pressures by the 'gold-standard' technique which can be useful in diagnosing conditions such as congestive heart failure, valve disease and diseases of the pericardium. Some patients develop shortness of breath after ablation procedures, and this can be prevented with assessment of intracardiac pressures after ablation. Although the purpose of this study is to assess the accuracy of these measurements from the ablation catheter, any unexpectedly abnormal patient findings such as elevated pressures or evidence of valve disease will be evaluated further per standard practice (echo, overnight observation, administering diuretic medications).

Potential benefits not to the subject include improved safety and monitoring during ablation procedures for future patients undergoing ablation.

**Data to be collected:** The patients' demographics, ablation indication, and prior echocardiogram study (when available) will be retrieved from chart review. The systolic, diastolic, and mean pressure values and waveform tracings for each heart chamber assessed will be collected during the procedure.

**Data Storage:** Data will be stored on Emory HIPAA compliant servers. All documents and information will be password protected with no information saved to personal computers.

**Patient selection:** Study patients will be recruited among all patients older than 18 years old undergoing elective ablation for an arrhythmia at Emory University Hospital. Up to 15 patients will be enrolled in order to obtain a minimum of 10 useable comparison datasets.

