**Informed Consent:** Following education on the study protocol, patients will be offered the option to enroll. Informed consent will be obtained by approved research personnel in a private area. If the patient agrees to participate, consent will be documented. Consent will occur the day of the scheduled ablation procedure.

**Compensation for time and effort:** There is no compensation for participation in this study. This research will add about 10 minutes to the standard of care procedure. .

**Data analysis:** The systolic, diastolic and mean pressure values for each chamber assessed will be compared between the RF ablation catheter derived measurement and the MPA catheter measurement. Measurements will be made in duplicate for each value. Comparison will be made using T – Test and a Kappa statistic.

Waveforms will be compared using a MACLAB system, by determining a mean gradient between the two waveforms. These values will be compared using a T –Test. All analyses will be performed using Microsoft Excel and Graphpad Prism.

**Safety:** Positioning of both catheters (ablation catheter and PA catheter ) will be done under continuous ultrasound guidance to ensure positioning of the catheter without secondary damage to the heart, heart valves or heart muscle. Fluoroscopy and 3-dimensional computer mapping will be used or immediately available for use in assisting positioning when needed. All catheter manipulation will be done by an experienced, Board certified cardiologist with greater than 10 years of experience in PA catheter manipulation and positioning [name].

The tip of the PA catheter has a balloon which will be inflated whenever advancing the balloon forward. This reduces risk of perforation as the catheter will bounce off the walls of the heart when encountered.

The catheter will be primarily position with use of guiding catheters which are already position in the chamber of interest(s) for the purpose of the catheter ablation procedure itself. This will also help minimize risk and time associated with PA catheter manipulation.

Equipment necessary to treat potential complications of catheter manipulation such as fluid or bleeding around the heart will be immediately available in the procedure suite. Operators will be experienced and qualified to perform stabilizing and treating procedures in case of such emergency.

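### Equivalence of the two catheters is hypothesised, but pressures are compared only by a T-test and an undefined Kappa, with no margin, interval rule or limits of agreement, so the planned analysis cannot establish it.

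*Combined protocol and SAP*

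**What the plan says.** The last paragraph of the Introduction/Background gives the purpose in these words: "test the hypothesis that transduction of intracardiac pressures using an irrigated ablation catheter placed as standard of care for the ablation procedure is equivalent". The comparator named there is the 5F balloon tipped PA catheter. The Objectives use a different word. The first is to "Determine accuracy of intracardiac pressure measurements as assessed by the balloon tipped pulmonary artery catheter and by an irrigated ablation catheter", with the PA catheter as the reference standard; the second asks the same about waveforms.

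Under Research Design both catheters are used in the same patient, one after the other, and "the ablation catheter will be serially positioned in the cardiac chambers (left OR right atrium, left OR right ventricle"). Patient selection gives the size: "Up to 15 patients will be enrolled in order to obtain a minimum of 10 useable comparison datasets". No calculation accompanies it.

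The Data analysis section states that "The systolic, diastolic and mean pressure values for each chamber assessed will be compared" between the two catheters, that each value is measured in duplicate, and then: "Comparison will be made using T – Test and a Kappa statistic". For waveforms, a mean gradient between the two tracings is obtained and examined by a T-test. Nothing further is said about how any result will be interpreted.

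**The concern.** An equivalence claim needs a statement of how large a difference would still be acceptable, and a rule that rules out larger ones. The plan has neither. Its T-test takes zero mean difference as the null hypothesis, so failing to reject it leaves the size of the difference open. With no other rule in the document, a reader of the results might take non-significance as agreement, and then noisier or fewer data would look more favourable.

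The T-test can mislead in the other direction too: a small, very consistent bias becomes significant even if it does not matter. It also concerns only the mean, so large errors of opposite sign in different patients cancel. Whether a single reading from the ablation catheter can stand in for a PA catheter reading depends on that scatter.

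The Introduction/Background itself expects bias to depend on the pressure examined, because dampening "may lead to underestimation of peak pressure and overestimation of the nadir pressure gradient". Bias therefore has to be estimated separately for each pressure.

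Kappa measures agreement between categories, and the pressures are continuous. The nearest thing to a category is in Risks/benefits, which refers to "any unexpectedly abnormal patient findings such as elevated pressures" as a trigger for clinical follow-up. It gives no cut-point and is not linked to Kappa.

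**Working it through.** **What can be reproduced.** The only design figure is 15 enrolled for at least 10 usable datasets. It cannot be re-derived, because the document gives no alpha, power, SD, effect size or margin. The calculations below are illustrations. From the document: n = 10 and n = 15, and the within-patient design. Assumed: the SD of the paired differences, the true bias, the 5 mmHg margin, a two-sided 5% T-test, and one difference per patient for a single pressure in a single chamber type.

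**1. A non-significant paired T-test.** With true bias b and SD of differences s, the statistic follows a non-central t distribution with n−1 degrees of freedom and non-centrality (b/s)√n. The miss rate is P(|T| < t(0.975, n−1)); the critical values are 2.262 (n = 10) and 2.145 (n = 15).

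- For b = 5, s = 5, n = 10, the non-centrality is 1 × √10 = 3.16.
- For b = 5, s = 10, n = 10, it is 0.5 × √10 = 1.58.

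| SD of differences (mmHg) | Missed 5 mmHg bias, n = 10 | n = 15 |
|---|---|---|
| 3 | 0.4% | under 0.1% |
| 5 | 20% | 5% |
| 8 | 58% | 38% |
| 10 | 71% | 56% |

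At SD 3 mmHg the test rarely misses such a bias. There the problem is the missing rule, not power.

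**2. A significant paired T-test.** With b = 1 mmHg and s = 1 mmHg, the non-centrality at n = 10 is again 3.16, so 80% of studies are significant. A 90% CI rule with a 5 mmHg margin would pass essentially all of those studies. The T-test answers only whether the mean difference is exactly zero.

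**3. Scatter between patients.** With zero bias and s = 5 mmHg, about 95% of individual differences lie within ±1.96 × 5 = ±9.8 mmHg. The T-test is significant only 5% of the time and gives no indication of that spread.

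**4. Kappa.** Simulated pairs with PA catheter values drawn from N(12, 6) and ablation values equal to the PA value plus N(0, s), without bias, unweighted Kappa:

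| Categories | s = 5 | s = 2 |
|---|---|---|
| One cut at 12 mmHg | 0.56 | 0.80 |
| One cut at 20 mmHg | 0.45 | 0.74 |
| Cuts at 5, 10, 15, 20 mmHg | 0.29 | 0.63 |
| 1 mmHg categories | 0.04 | 0.16 |

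Within a column the agreement between catheters is identical; only the cut-points change.

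**5. What the planned data could support.** Equivalence is claimed if |mean| + t(0.95, n−1) × s/√n < 5 mmHg, where s here is the sample SD (two one-sided tests at 5%). At a sample SD of 5 mmHg and n = 10 the half-width is 1.833 × 5/√10 = 2.9 mmHg, so the observed mean must lie within ±2.1 mmHg. Integrating over the distribution of the sample SD, at zero true bias:

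| True SD (mmHg) | Pass rate, n = 10 | n = 15 |
|---|---|---|
| 5 | 80% | 96% |
| 8 | 21% | 49% |

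Each limit of agreement would have a 95% CI half-width of t(0.975, n−1) × s × √(1/n + 1.96²/(2(n−1))). That is 1.27 s at n = 10 and 0.97 s at n = 15, or about 6.3 and 4.8 mmHg at s = 5.

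**The case against.** The strongest reply is that this is a small study whose Objectives speak of accuracy, and Risks/benefits also describes its purpose as assessing accuracy. Accuracy can be served by estimation without any margin. That stands: the absence of a margin bears on the equivalence hypothesis in the Introduction/Background. The accuracy objectives still lack a suitable method, because a T-test and Kappa estimate neither the limits of agreement nor their precision.

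Several stronger readings are tempting, and the document does not support them.

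- **That non-significance will be declared equivalence.** The document does not say so. The miss rates in step 1 do harm only under that reading; what can be said is that no alternative rule is offered.
- **That the study could never show equivalence, or never count against it.** The limitation lies in the analysis. Paired, duplicate data could support an equivalence rule fixed in advance, and a large consistent difference would still be evidence against the hypothesis.
- **That an unpaired test is planned.** The T-test is not described as paired, but both catheters are used in the same patient and the same chambers, so a paired analysis is the natural reading. It needs only to be stated.
- **That the plan is silent on pooling left and right chambers.** The phrase about each chamber assessed can be read as separate analyses, while Research Design treats pressures as similar enough not to sample all four chambers. The text is ambiguous.
- **That a formal criterion on the limits of agreement is indispensable.** It is a stricter option. With limits required within ±10 mmHg, the pass rate at n = 10 and SD 5 falls from about 80% to 39%, largely because the true limits of ±9.8 mmHg sit at that boundary.

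**Conclusion.** The concern holds for the planned analysis. An equivalence hypothesis is paired with a T-test of the mean and a Kappa without categories, and no statement links any result to equivalence. This is an unsuitable method rather than a missing detail, and it should be corrected before the study is used to support the hypothesis.

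The conclusion rests on the text and not on the illustrative figures. Those show the possible size: with 10 pairs, the chance of overlooking a 5 mmHg bias runs from 0.4% at SD 3 mmHg to 71% at SD 10 mmHg, and a 1 mmHg bias at SD 1 mmHg is flagged in 80% of studies. Every SD, bias and margin used is an assumption.

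**What to change.** Rewrite the Data analysis paragraph as follows.

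- Analyse within-patient differences (ablation minus PA catheter). For each pressure and chamber type, report the Bland-Altman bias and 95% limits of agreement, each with confidence intervals.
- Before enrolment, name the pressure(s) and chamber(s) on which an equivalence claim rests, and set a justified mmHg margin for each.
- Claim equivalence only if the 90% CI of the mean paired difference lies inside the margin, read alongside the reported limits of agreement. A formal criterion on the limits is optional.
- Otherwise report agreement estimates and make no equivalence claim. State that a non-significant T-test will not be read as equivalence, for pressures or for waveforms.
- Drop Kappa, or tie it to categories fixed in advance.
- Average the duplicates within patient or model them, and say which.
- State whether left and right chambers are analysed separately or pooled.

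No extra measurements are needed. The harder work is justifying the margins, since one value may not suit systolic, diastolic and mean pressures in both atria and ventricles. The main downside is that 10 to 15 patients may leave the result inconclusive, as the 21% and 49% pass rates at SD 8 mmHg show. In that case the study reports estimates of agreement only.

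### Kappa, a statistic for categories, is the planned agreement measure for continuous pressure values, and no categories, cut-points or weights are defined

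*Combined protocol and SAP*

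**What the plan says.** The hypothesis in the Introduction/Background is that pressure transduced through the irrigated ablation catheter "is equivalent to transduction of pressures using a standard 5F balloon tipped PA catheter placed only for this research study". The first item under Objectives is to "Determine accuracy of intracardiac pressure measurements as assessed by the balloon tipped pulmonary artery catheter and by an irrigated ablation catheter".

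The Data to be collected section describes numeric readings: "The systolic, diastolic, and mean pressure values and waveform tracings for each heart chamber assessed will be collected during the procedure". The Data analysis section then states: "The systolic, diastolic and mean pressure values for each chamber assessed will be compared between the RF ablation catheter derived measurement and the MPA catheter". It adds "Measurements will be made in duplicate for each value", and names the methods: "Comparison will be made using T – Test and a Kappa statistic".

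Under Patient selection, "Up to 15 patients will be enrolled in order to obtain a minimum of 10 useable comparison datasets".

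No section defines a pressure category, a normal/abnormal cut-point, a weighting scheme or a threshold for reading Kappa. No Bland-Altman analysis, intraclass correlation or concordance correlation is planned.

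**The concern.** Kappa is chance-corrected agreement on a categorical scale. To apply it to continuous pressures, the analyst must make a choice that the plan does not make.

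- **Raw readings, no weights.** Each distinct value becomes its own category. Only exact matches count, so a 1-unit miss is penalised as heavily as a 40-unit miss.
- **Readings binned first.** The result depends on where the cut is placed, and with no cut in the plan it would be chosen after the data are seen. Any bias that moves no patient across the cut is invisible.

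Neither form reports agreement in pressure units. Yet the Introduction/Background expects an error in exactly those units: damping that lowers the peak and raises the nadir. The first form can make a closely agreeing catheter look poor. The second can make a biased one look perfect.

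**Working it through.** The plan gives no figure to reproduce: it states no SD, margin, cut-point or expected Kappa. From the documents I take the statistic (Kappa, unspecified), the data type (numeric pressures) and the sample size (10 to 15). Pressure levels, SDs, errors and the cut-point below are assumptions. The unit is presumably mmHg, but the documents do not say.

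**Formulas.** Kappa = (Po − Pe)/(1 − Pe), where Po is the observed proportion of identical categories and Pe the proportion expected by chance. Concordance correlation (CCC) = 2·cov(x,y) / [var(x) + var(y) + (mean x − mean y)²].

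**Example 1: close agreement, Kappa zero.** Ten reference values 100, 104, …, 136. The second catheter reads alternately +1 and −1 (101, 103, 109, 111, …, 135).
- No pair matches, so Po = 0. No value occurs in both lists, so Pe = 0. Kappa = 0.00.
- Variances are 132 and 129, the covariance is 130 and the mean difference is 0. CCC = 260/261 = 0.996.

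**Example 2: real bias, Kappa perfect.** Reference values 5, 6, 6, 7, 8, 18, 19, 20, 22, 24. The second catheter reads 4 higher throughout. Cut at 15.
- Both catheters put five patients below and five above, and they are the same patients. Po = 1, Pe = 0.5, Kappa = 0.5/0.5 = 1.00, with a bias of 4.0.
- Unweighted Kappa on the same raw values: Po = 0; the values 22 and 24 each occur once in both lists, so Pe = 2 × 0.1 × 0.1 = 0.02. Kappa = −0.02/0.98 = −0.02.

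The same data thus give 1.00 or −0.02, depending on a choice the plan leaves open.

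**Simulation, raw readings** (n = 10, rounded to whole units, 4,000 runs per setting, means):

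| Between-patient SD | Offset | SD of differences | Unweighted Kappa | CCC |
|---|---|---|---|---|
| 20 | 0 | 1 | 0.34 | 1.00 |
| 20 | 0 | 2 | 0.17 | 0.99 |
| 20 | 2 | 0.5 | −0.01 | 0.99 |
| 5 | 0 | 1 | 0.31 | 0.97 |
| 5 | 0 | 2 | 0.14 | 0.90 |
| 5 | 2 | 0.5 | −0.05 | 0.89 |

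At n = 15 the Kappas are essentially unchanged.

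**Binned readings** (assumed mean 120, SD 20, cut 130, constant under-reading, n = 10). A patient changes category only if the reference value lies between 130 and 130 plus the offset.
- Offset 5: Φ(0.75) − Φ(0.50) = 0.7734 − 0.6915 = 0.0819. No patient of ten changes with probability 0.9181¹⁰ = 0.43.
- Offset 8: Φ(0.90) − Φ(0.50) = 0.8159 − 0.6915 = 0.1245. No patient changes with probability 0.8755¹⁰ = 0.26.

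These figures include studies in which all ten patients fall on one side of the cut and Kappa is undefined, about 0.6915¹⁰ = 0.025. A Kappa of exactly 1 therefore occurs in about 40% and 24% of studies.

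**The case against.** Five points can be made for the plan.

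1. **The text does not say unweighted.** Quadratic-weighted Kappa on the raw values behaves like the CCC (0.996 in Example 1). This is true, but the plan specifies no weights, so the good behaviour of one unstated variant does not rescue it.
2. **The two failures belong to different readings.** Zero Kappa needs raw values; perfect Kappa despite bias needs binning, which the plan does not mention. This stands, and the figures must be read that way. Zero is also the extreme case: with purely random error of SD 0.5 to 2, median Kappa was about 0.14 to 0.58, still well below the actual agreement.
3. **In the binned case Kappa usually does fall below 1.** This stands. For offsets of 5 and 8, mean Kappa where defined was 0.76 and 0.63.
4. **The t-test would catch an offset.** A paired test at n = 10 detects 2 units (difference SD 0.5) or 5 units (difference SD 2) in essentially every simulated study. But the plan does not say the test is paired, and an unpaired test with between-patient SD 20 detects almost none. Either version addresses only the mean, not the spread of individual differences, and a non-significant result in 10 to 15 patients does not show equivalence.
5. **The plan also computes a mean gradient between waveforms.** It does, for the second objective. For the pressure values, Kappa remains the only agreement measure. No decision rule is attached to it, so the harm is a misleading summary and not an automatic wrong decision.

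**Conclusion.** The concern holds. As written, the plan applies a categorical statistic to continuous pressures without the definitions that would make it computable in a single way, in a study whose hypothesis is equivalence and whose first objective is accuracy. The mismatch itself follows from the text and needs no assumption.

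Its size depends on the reading. Unweighted on raw values, Kappa is about 0.14 to 0.34 when the catheters differ only by random error of SD 1 to 2 units and the CCC is 0.90 or higher. Binned under the assumed mean, SD and cut, Kappa shows no disagreement in about 43% of ten-patient studies with a 5-unit bias and 26% with an 8-unit bias. The binned percentages would change with other levels and cut-points, which vary by chamber. The pressure readings themselves are unaffected and can be reanalysed.

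**What to change.** Remove Kappa for the pressure values. For each pressure type and chamber, report the mean difference between catheters and the Bland-Altman 95% limits of agreement (mean ± 1.96 SD of the differences), both with confidence intervals. Three details need stating:

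- **Acceptable difference.** The investigators should fix, before analysis, the difference that counts as equivalent. Without it the limits describe agreement but cannot answer the hypothesis.
- **Duplicates and chambers.** If the two readings per catheter are averaged, limits for a single reading need the within-catheter variance added back: var(d) = var(difference of means) + ½·s²(ablation) + ½·s²(PA). Analyse chambers separately, or use a model with a patient effect if they are pooled.
- **Secondary summaries.** A concordance or absolute-agreement intraclass correlation may be added, but not alone: the CCC was still 0.99 with a 2-unit offset at SD 20. If a clinical classification is of interest, define the cut-off in advance and report Kappa for that classification only, stating any weights.

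The limits will be imprecise. The standard error of each is about SD·√[1/n + 1.96²/(2(n − 1))]. That is 0.56 SD at n = 10 (√(0.100 + 0.213)) and 0.45 SD at n = 15 (√(0.067 + 0.137)), and this should be reported.

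The cost is a few sentences in Data analysis and one decision on the acceptable difference. No additional measurements or patients are needed.
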